7.10 Other Outcomes (Secondary Endpoints and Exploratory Endpoints)

Other secondary endpoints include change from baseline to final visit of treatment period in Urine Protein to Creatinine Ratio (UPCR), serum creatinine (SCr) level and estimated glomerular filtration rate (eGFR) measurement.

Observed values of UPCR, SCr and eGFR will be listed for each subject by visit. Baseline, final visit values and change from baseline at final visit will be summarized by pooled placebo, ixazomib dose and ixazomib overall (N, mean, SD, median, minimum and maximum) using the safety set.

Due to the fact that the study was terminated before the finalization of this statistical analysis plan, no summaries nor analysis will be performed for the exploratory endpoints. Data collected on eCRF or from study procedures that are related to the exploratory endpoints will be listed if appropriate.

7.11 Safety Analysis

Safety measures include AEs, clinical laboratory parameters, vital sign parameters, 12-lead ECG results, and other safety parameters. The safety analysis set will be used for all summaries of safety parameters.

7.11.1 Adverse Events

A Pre-Treatment Event (PTE) is defined as any untoward medical occurrence in a clinical investigation subject who has signed informed consent to participate in a study, but prior to administration of any study medication; it does not necessarily have to have a causal relationship with study participation.

An AE is defined as any untoward medical occurrence in a clinical investigation subject administered a drug; it does not necessarily have to have a causal relationship with this treatment. PTE and AE verbatim terms will be coded by SOC and PT using MedDRA (version 20.0 or later).

Treatment-Emergent Adverse Events (TEAE)s will be defined as AEs that occur after the first dose of study drug received in the treatment period and up to 30 days (onset date – last date of dose + 1 ≤ 30) after the last dose of study drug or early termination.

TEAEs will be presented by severity (mild, moderate, and severe). Serious TEAEs, TEAEs leading to study drug discontinuation, and TEAEs leading to death will also be summarized using SOC and PT.

When calculating the frequency and percentage of subjects who reported TEAEs, a subject will be counted only once for each SOC or PT when multiple TEAEs are coded to the same SOC or PT. For the intensity or relatedness summaries, if a subject reports multiple TEAEs coded to the same SOC or PT, the TEAE with maximum intensity or strongest relationship will be included in the summary.

AEs with missing severity will be listed as such in the AE listings, however, will be summarized as severe in summary tables. Similarly, if the relationship of an event is missing, the event will be considered as related but in listings it will be presented as missing.

In general, AEs will be tabulated at the following levels: overall summary (subjects with at least 1 AE in any dose or treatment), the MedDRA SOC, and the MedDRA PT. The tables will

include the number and percentage (N[%]) of subjects. The following summary tables will be generated for all cohorts:

- Overview of Treatment-Emergent Adverse Events.
- Treatment-Emergent Adverse Events by System Organ Class and Preferred Term.
- Serious Treatment-Emergent Adverse Events by System Organ Class and Preferred Term.
- Most Frequent (>5% or N>2) Non-Serious Adverse Events by Preferred Term.
- Most Frequent (>5% or N>2) Non-Serious Adverse Events by System Organ Class and Preferred Term.
- Relationship of Treatment-Emergent Adverse Events to Study Drug by System Organ Class and Preferred Term.
- Drug-Related Treatment-Emergent Adverse Events by System Organ Class and Preferred Term.
- Severity of Treatment-Emergent Adverse Events by System Organ Class and Preferred Term.

In addition, the following summary tables, number and percentage of subjects, will be generated for the following primary endpoints in all cohorts:

- At least 1 Grade ≥ 2 treatment emergent adverse event (TEAE) according to CTCAE.

Subject mappings for the TEAEs by SOC and PT will be generated.

Data listings will be provided for PTEs, TEAEs, TEAEs leading to study drug discontinuation AEs leading to discontinuation of investigational study medication, SAEs and AEs that resulted in death.

7.11.2 Clinical Laboratory Evaluations

Clinical laboratory tests will be assessed using the safety analysis set and will be evaluated and presented using International System of Units (SI) unless otherwise stated. [Table 7.a](#) shows a list of all clinical laboratory tests.

Table 7.a Clinical Laboratory Tests

Hematology	Serum Chemistry	Urinalysis	Special
Red blood cells	Alanine aminotransferase	To be done at local laboratory	To be done at local laboratory
Reticulocytes	Alkaline phosphatase		
White blood cells with differential	Aspartate aminotransferase	pH	Coomb's test
Hemoglobin	γ-Glutamyl transferase	Specific gravity	Platelets, red blood cells, white blood cells with differential
Hematocrit	Total bilirubin	Protein	
Platelets	Direct bilirubin	Glucose	
	Albumin	Blood	To be done at central laboratory
	Total protein	Nitrite	
	Creatinine	Microscopic Analysis:	Lipid panel (fasted):
	Blood urea nitrogen	RBC/high power field	Total cholesterol
	Creatine kinase	WBC/high power field	LDL-cholesterol
	Potassium	Epithelial cells, casts, etc	HDL-cholesterol
	Sodium		Triglycerides
	Glucose	To be done at central laboratory	Serum complement
	Chloride	Urine protein and creatinine for UPCR	C3 and C4
	Phosphorus	Urine Biomarkers	Total IgM, IgG and IgA
	Calcium	To be done at the site	Autoantibodies:
		Standard urinalysis using dipstick (protein only)	Anti-double-stranded DNA
			Anti-nuclear antibody
			Anti-Ro (SS-A)
			Anti-La (SS-B)
			Anti-RNP
			Anti-Sm
			Anti-phospholipids
			Serum biomarkers
			Tetanus antibody titers
			HBsAb titers

Serum

Serum hCG (a)

At Screening Only:

Hepatitis panel, including HBsAg, anti-HCV and HIV

FSH (b)

DNA=deoxyribonucleic acid, FSH=follicle-stimulating hormone, HBsAb=hepatitis B surface antibody, hCG=human chorionic gonadotropin, HDL=high-density lipoprotein, HIV=human immunodeficiency virus, LDL=low-density lipoprotein.

(a) Serum hCG pregnancy test will be done on all female subjects of childbearing potential at Screening.

(b) The FSH level will be obtained for female subjects at Screening if they are postmenopausal by history (ie, last regular menstrual cycle >2 years) and not surgically sterile. The FSH result must be >40 IU/L for the subject to be permitted not to use adequate contraception.

All laboratory test parameters will be displayed in individual subject data listings in both SI units and conventional (CV) units. For test results not in SI units, the conversion to SI units will be done in derived analysis data sets using the known conversion factors. If necessary, SI units from the central laboratory may be converted to Takeda's preferred SI units in the derived dataset. All summaries and analyses will be based on the values using these preferred SI units.

Descriptive statistics (N, mean, SD, median, minimum, and maximum) for the observed baseline, post-baseline and change from baseline values will be presented by pooled placebo group, ixazomib doses, and ixazomib overall for the following laboratory tests:

- Red blood cells.
- White blood cells with differential.
- Platelets.
- Alanine aminotransferase.
- Alkaline phosphatase.
- Aspartate aminotransferase.
- γ -Glutamyl transferase.
- Total bilirubin.
- Creatinine.
- Blood urine nitrogen.
- Urine protein and creatinine for UPCR.
- C3 and C4.
- Total IgM, IgG and IgA.
- Anti-double-stranded DNA.
- Tetanus antibody titers.
- HBsAb titers.

Study baseline will be used for change from baseline.

Laboratory Markedly Abnormal Values (MAVs), identified by the criteria defined in [Appendix A](#), will be tabulated. If a subject has a MAV for a particular laboratory test, all visits for that subject for that parameter will be listed. The number and percentage of subjects with at least 1 post-dose markedly abnormal laboratory test result will be summarized. The mapping of the subjects who meet the MAV criteria will be listed as a table. All observations, including ones at unscheduled visits, will be included in the MAV evaluation and summaries if MAV criteria are satisfied.

All clinical laboratory data will be presented in both SI and conventional units in data listings.

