5.1.1 Primary Endpoint

- Percentage of study subjects with at least 1 Grade ≥ 2 treatment emergent adverse event (TEAE) according to CTCAE.
- Percentage of study subjects with at least 1 serious adverse event (SAE).
- Percentage of study subjects with at least 1 adverse event leading to discontinuation of investigational study medication.
- Percentage of subjects with at least 1 markedly abnormal laboratory criteria for hematologic parameters.

[figure not shown]

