Appendix A Criteria for Identification of Markedly Abnormal Laboratory Values
Hematology – Criteria for Markedly Abnormal Values (SI units)

Parameter	Unit	Low Abnormal	High Abnormal
Hemoglobin	Both	$< 0.8 \times \text{LLN}$	$> 1.2 \times \text{ULN}$
Hematocrit	Both	$< 0.8 \times \text{LLN}$	$> 1.2 \times \text{ULN}$
RBC count	Both	$< 0.8 \times \text{LLN}$	$> 1.2 \times \text{ULN}$
WBC count	Both	$< 0.5 \times \text{LLN}$	$> 1.5 \times \text{ULN}$
Platelet count	Conventional	$< 75 \times 10^3/\mu\text{L}$	$> 600 \times 10^3/\mu\text{L}$
	SI	$< 75 \times 10^9/\text{L}$	$> 600 \times 10^9/\text{L}$
Reticulocytes	Conventional	--	$> 3\%$ of erythrocytes
	SI	--	> 0.030 Fraction of 1

LLN=lower limit of normal, RBC=red blood cell, ULN=upper limit of normal, WBC=white blood cell.

Serum Chemistry – Criteria for Markedly Abnormal Values (SI units)

Parameter	Unit	Low Abnormal	High Abnormal
ALT	Both	--	>3 × ULN
AST	Both	--	>3 × ULN
GGT	Both	--	>3 × ULN
Alkaline phosphatase	Both	--	>3 × ULN
Calcium	Conventional	<7.0 mg/dL	>11.5 mg/dL
	SI	<1.75 mmol/L	>2.88 mmol/L
Chloride	Conventional	<75 mEq/L	>126 mEq/L
	SI	<75 mmol/L	>126 mmol/L
Total bilirubin	Conventional	--	>2.0 mg/dL
	SI	--	>34.2 µmol/L
Albumin	Conventional	<2.5 g/dL	--
	SI	<25 g/L	--
Total protein	Both	<0.8 × LLN	>1.2 × ULN
Creatinine	Conventional	--	>2.0 mg/dL
	SI	--	>177 µmol/L
Blood urea nitrogen	Conventional	--	>30 mg/dL
	SI	--	>10.7 mmol/L
Sodium	Conventional	<130 mEq/L	>150 mEq/L
	SI	<130 mmol/L	>150 mmol/L
Potassium	Conventional	<3.0 mEq/L	>6.0 mEq/L
	SI	<3.0 mmol/L	>6.0 mmol/L
Glucose	Conventional	< 50 mg/dL	>350 mg/dL
	SI	< 2.8 mmol/L	>19.4 mmol/L
Bicarbonate	Conventional	<8.0 mEq/L	--
	SI	<8.0 mmol/L	--
Creatine kinase	Conventional	--	>5 × ULN
	SI	--	>5 × ULN
Total Cholesterol	Conventional	--	>300 mg/dL
	SI	--	>7.72 mmol/L
Triglycerides	Both	--	>2.5 × ULN
LDL Cholesterol	Conventional	< 50 mg/dL	>160 mg/dL
	SI	<1.30 mmol/L	>4.14 mmol/L
HDL Cholesterol	Conventional	<40 mg/DL	>60mg/DL
	SI	<1.04 mmol/L	>1.55 mmol/L
Direct Bilirubin	Conventional	--	>2 x ULN
Phosphorus	Conventional	<1.6mg/dL	>6.2 mg/dL
	SI	<0.52 mmol/L	>2mmol/L

ALT=alanine aminotransferase, AST=aspartate aminotransferase, GGT=γ-glutamyl transferase, LLN=lower limit of normal, ULN=upper limit of normal.

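### The fixed list of summarized laboratory tests in SAP 7.11.2 omits hemoglobin (with hematocrit and reticulocytes), so a hemoglobin fall that stays above 0.8 × LLN reaches no laboratory summary table

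*SAP*

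**What the plan says.** SAP 7.11.2 says that Table 7.a "shows a list of all clinical laboratory tests". Its hematology column has six entries: red blood cells, reticulocytes, white blood cells with differential, hemoglobin, hematocrit and platelets.

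The same section then sets out the descriptive table: "Descriptive statistics (N, mean, SD, median, minimum, and maximum) for the observed baseline, post-baseline and change from baseline values will be presented". Its scope is limited by the words "will be presented by pooled placebo group, ixazomib doses, and ixazomib overall for the following laboratory tests", followed by 16 entries. Nothing in the wording marks these as examples, so the list is closed. Three hematology entries are on it: red blood cells, white blood cells with differential, and platelets.

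The only other laboratory summary is the MAV table: "The number and percentage of subjects with at least 1 post-dose markedly abnormal laboratory test result will be summarized". Appendix A supplies the limits. Hemoglobin and hematocrit count as low below 0.8 × LLN and as high above 1.2 × ULN. Reticulocytes have a high limit only ("> 0.030 Fraction of 1" in SI units).

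SAP 5.1.1 makes the percentage of subjects meeting "markedly abnormal laboratory criteria for hematologic parameters" one of four primary endpoints. Individual values are kept: "All laboratory test parameters will be displayed in individual subject data listings".

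**The concern.** The primary objective is safety and tolerability, and one primary endpoint is built on hematology. Appendix A treats hemoglobin, hematocrit and reticulocytes as hematologic parameters, yet the plan gives none of them a mean, median or change from baseline by group. Tetanus and HBsAb titers, which belong to no primary endpoint, do get such a summary.

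The MAV table answers a different question. It counts subjects who cross a fixed limit and, for hemoglobin, has no change-from-baseline term. A shift of a whole dose group that stops short of the limit leaves the count at zero. No laboratory shift table is planned that would show it. At stake is whether the report's laboratory tables would show a moderate, dose-related fall in hemoglobin.

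**Working it through.** The plan gives no figure to reproduce here. The check has two parts: a comparison of lists, and an illustration of how large a fall can go untabulated.

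**Comparison of lists** (Table 7.a, the 7.11.2 list, Appendix A)

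| Hematology test in Table 7.a | Descriptive summary in 7.11.2 | MAV limit in Appendix A |
|---|---|---|
| Red blood cells | Yes | Low and high |
| White blood cells with differential | Yes | Low and high (WBC count) |
| Platelets | Yes | Low and high |
| Hemoglobin | No | Low and high |
| Hematocrit | No | Low and high |
| Reticulocytes | No | High only |

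Summarized: 3 of 6. Not summarized: hemoglobin, hematocrit, reticulocytes.

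The list is also selective outside hematology. Table 7.a has 17 serum chemistry tests, of which 7 are on the list and 10 are not: direct bilirubin, albumin, total protein, creatine kinase, potassium, sodium, glucose, chloride, phosphorus and calcium.

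SAP 7.13 names the reductions made because of early termination: Cohorts A and B only, the double-blind period only, no exploratory summaries, and no PK parameters. The short laboratory list is not among them.

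**Size of an untabulated hemoglobin fall**

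The SAP gives no LLN. Assume 110 to 135 g/L. The low MAV limit is 0.8 × LLN, and the largest fall that is not flagged is baseline − 0.8 × LLN.

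| Assumed LLN (g/L) | 0.8 × LLN (g/L) | Largest unflagged fall from baseline = LLN | Largest unflagged fall from baseline = 140 g/L |
|---|---|---|---|
| 110 | 88 | 22 (20%) | 52 (37.1%) |
| 115 | 92 | 23 (20%) | 48 (34.3%) |
| 120 | 96 | 24 (20%) | 44 (31.4%) |
| 130 | 104 | 26 (20%) | 36 (25.7%) |
| 135 | 108 | 27 (20%) | 32 (22.9%) |

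One worked case at LLN 120: a fall from 130 to 97 g/L is 33 g/L, and 33/130 = 25.4%. Since 97 > 96, it is not a hemoglobin MAV. SAP 6.0 plans at least 4 active subjects in each of Cohorts A and B. If all 4 in a cohort did this, the hemoglobin MAV row would read 0/4 = 0%, and no hemoglobin change statistic would stand beside it.

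For reticulocytes, no fall of any size can meet a criterion, because Appendix A has no low limit.

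**The case against.** The strongest reply is that little information is lost.

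- Every laboratory value is listed by subject in both unit systems. With Cohorts A and B planned at a minimum of 2 × (4 + 1) = 10 subjects, a reader can follow each hemoglobin course by eye. This stands. A reader might infer that the report could not describe a hemoglobin fall at all, but the listings rule that out. What is missing is the group summary.
- A fall that the investigator reports as an adverse event enters the treatment-emergent tables by class and term, severity and relationship. If it is Grade 2 or above, it also enters the CTCAE primary endpoint table. This stands too, although it depends on the event being reported. The gap is confined to laboratory tables.
- A reader might also infer that a primary endpoint is damaged. It is not. The endpoint in 5.1.1 counts marked abnormalities, Appendix A covers the three tests, and no result for that endpoint changes. The SAP does not say that the endpoint is meant to capture falls above the limit.
- The list looks chosen. It drops ten chemistry tests as well, and its three hematology entries match the local-laboratory blood count entry in the Special column of Table 7.a. That is plausible, but the SAP states no reason, and the omitted chemistry tests do not feed the hematologic endpoint.
- Red cell count is summarized with change from baseline. It is a partial stand-in, but the SAP does not say how closely it tracks hemoglobin.
- The case of four subjects all stopping at 97 g/L is constructed. It shows what the rule permits and does not predict what happened.

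**Conclusion.** The point holds as a minor gap in the laboratory summaries. Followed as written, 7.11.2 yields no group summary of hemoglobin, hematocrit or reticulocytes, and a hemoglobin fall that stays above 0.8 × LLN appears in no laboratory summary table. The omission itself, 3 of 6 hematology tests, rests on the text alone. The size of the fall rests on the assumed LLN of 110 to 135 g/L: 20% from a baseline at the LLN, and about 23% to 37% from 140 g/L.

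The severity is low because the study is small, unpowered and terminated early, and has full subject listings. The change is still worth making, because it serves the primary safety objective at almost no cost.

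**What to change.** Add hemoglobin to the list of summarized tests in SAP 7.11.2, and hematocrit and reticulocytes for completeness. Observed baseline, post-baseline and change-from-baseline values would then be reported for pooled placebo, each ixazomib dose and ixazomib overall, in the table format already planned. Coverage of the Table 7.a hematology column goes from 3 of 6 to 6 of 6. If the omission was intended, 7.13 should say so and give the reason.

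No separate analysis of the lowest post-dose value is needed. The cost is about one line of SAP wording and three more tests in an existing table, with no new data and no new derivation.

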Appendix C Criteria for Markedly Abnormal 12-Lead ECG Parameters

Parameter	Unit	Lower Criteria	Upper Criteria
Heart Rate	bpm	< 50	> 120
PR	msec	≤ 80	≥ 200
RR	msec	≤ 600	≥ 1440
QRS	msec	≤ 80	≥ 180
QT Interval	msec	≤ 50	≥ 460
QTcB Interval	msec	≤ 50	≥ 500 OR ≥ 30 change from baseline and ≥ 450
QTcF Interval	msec	≤ 50	≥ 500 OR ≥ 30 change from baseline and ≥ 450

ELECTRONIC SIGNATURES

Signed by	Meaning of Signature	Server Date (dd-MMM-yyyy HH:mm 'UTC')
Personal Protected Information	Biostatistics Approval	07-Mar-2018 18:01 UTC
	Pharmacovigilance Approval	07-Mar-2018 18:27 UTC
	Clinical Approval	07-Mar-2018 18:35 UTC
	Clinical Pharmacology Approval	07-Mar-2018 19:39 UTC
	Biostatistics Approval	08-Mar-2018 15:02 UTC

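### The hematologic MAV primary endpoint counts abnormalities persisting from baseline together with new ones, and no planned laboratory table or flag separates them

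*SAP*

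**What the plan says.** SAP 5.1.1 lists as its fourth primary endpoint: "Percentage of subjects with at least 1 markedly abnormal laboratory criteria for hematologic parameters". It gives no timing and no condition on the subject's baseline.

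SAP 7.11.2 supplies the counting rule: "The number and percentage of subjects with at least 1 post-dose markedly abnormal laboratory test result will be summarized". It adds: "All observations, including ones at unscheduled visits, will be included in the MAV evaluation and summaries if MAV criteria are satisfied". The population is fixed by "Clinical laboratory tests will be assessed using the safety analysis set".

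Appendix A sets the hematology limits. Hemoglobin, hematocrit, RBC and WBC use multiples of LLN and ULN. Platelets and reticulocytes use absolute values.

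The other laboratory outputs in 7.11.2 are:
- descriptive statistics "for the observed baseline, post-baseline and change from baseline values will be presented by pooled placebo group", ixazomib dose and ixazomib overall, for a named list of tests;
- a listing of all visits for the affected parameter in any subject with a MAV, and listings of all laboratory data;
- a subject mapping: "The mapping of the subjects who meet the MAV criteria will be listed as a table".

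Section 7.1 defines baseline as the last value observed before the first dose. Section 6.0 states that the study is not powered for any hypothesis test. Section 7.13 restricts reporting to Cohorts A and B in the double-blind period.

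**The concern.** The primary objective (4.1) is to characterize the safety and tolerability of ixazomib. A hematologic MAV that was there before dosing and simply continues says little about the drug, yet it enters the primary-endpoint percentage with the same weight as a new one. Someone reading only the summary table cannot tell which kind was counted.

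Elsewhere the SAP does take account of onset or baseline. The Grade ≥ 2 adverse event endpoint in 5.1.1 is limited to treatment-emergent events. ECG interpretation, which belongs to the additional safety assessments, gets a cross-tabulation of baseline against each later visit (7.11.4). The hematologic primary endpoint has neither.

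What is at stake is how one descriptive percentage is read. No test, error rate or power is affected.

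**Working it through.** The SAP gives no figure to reproduce here, so the check sets the rules against each other and then sizes the effect.

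**Step 1: do the limits refer to baseline?** Appendix A has six hematology parameters. Five have a low and a high limit and reticulocytes have a high limit only, so there are 5 × 2 + 1 = 11 limits. None refers to the subject's baseline. Across Appendices A to C, only QTcB and QTcF have such a limb ("≥ 500 OR ≥ 30 change from baseline and ≥ 450"). Even there, the ≥ 500 limb stands without a baseline condition.

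**Step 2: what does the rule do?** Take a subject whose hemoglobin is just below 0.8 × LLN before the first dose and at the same level afterwards. The post-dose value meets the limit, so the subject is counted.

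**Step 3: does another planned laboratory output separate the two kinds?**
- MAV count table: no.
- Descriptive tables: these are group statistics and in general cannot classify a subject. They cover RBC, WBC and platelets but not hemoglobin, hematocrit or reticulocytes, which are 3 of the 6 parameters.
- Subject mapping: no baseline flag is stated, and nothing says whether it is limited to post-dose values.
- Laboratory shift table: none is planned.
- All-visit listing: yes, by reading case by case.

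**Step 4: weight of one subject.** Section 6.0 plans at least 4 active and 1 placebo subjects in each of Cohorts A and B. That gives 4 + 4 = 8 active, 1 + 1 = 2 pooled placebo and 10 in all. One subject counted only for a persisting MAV moves the percentage by:
- 1/4 = 25 points in a dose group;
- 1/8 = 12.5 points in ixazomib overall;
- 1/2 = 50 points in pooled placebo.

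**Step 5: how likely is such a case?** The SAP does not say. Let q be the assumed chance that a subject has a persisting baseline MAV and no new one, with subjects independent. The mean contribution to the percentage is 100q points. The chance of at least one such subject among n is 1 − (1 − q)^n.

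| Assumed q | Mean contribution | n = 8 (ixazomib) | n = 10 (all) |
|---|---|---|---|
| 2% | 2 points | 15% | 18% |
| 5% | 5 points | 34% | 40% |
| 10% | 10 points | 57% | 65% |
| 20% | 20 points | 83% | 89% |

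For example, q = 5% and n = 8 gives 1 − 0.95^8 = 0.337. These rows show a range and do not estimate q.

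**The case against.** The strongest reply is that nothing here is wrong. The endpoint asks for at least one MAV, the rule counts at least one post-dose MAV, and an inclusive count is usual. With about 10 planned subjects, the all-visit listings let a reader sort new from persisting cases completely. All of this stands.

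Three further points also stand:
- The baseline minimum and maximum help for platelets. If a group's baseline range lies within 75 and 600 × 10^9/L, every platelet MAV in that group is new. The check is only indirect for RBC and WBC, whose limits depend on LLN and ULN, and is not available for the other three parameters.
- The 25, 12.5 and 50 point steps are 1/n and would apply to any event. The rule adds only that a step need not reflect a new event.
- A full cross-table of baseline against post-dose status, one line per limit, would largely repeat the listings in an SAP already cut back after early termination.

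A reader might go further and infer that the endpoint is inflated, or that the comparison with placebo is biased. The SAP supports neither. Measured against 5.1.1 the count is what was specified. If q were the same in every group, the expected active-minus-placebo difference would not change.

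What the reply does not remove is that the summarized percentage mixes the two kinds, and nothing planned in the tables alerts its reader.

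**Conclusion.** The point holds as a minor, cheap improvement. The hematologic MAV percentage does not distinguish new from persisting abnormalities, and no planned laboratory table or flag does so. It is not a contradiction and no information is lost, because the listings keep every case traceable.

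Its size cannot be fixed from the SAP. One such subject is worth 25, 12.5 or 50 points at the planned minimums. Section 6.0 says at least, so larger actual groups would give smaller steps. The frequency is an assumption throughout: eligibility limits in the protocol, which is not at hand, may bring it near 0, in which case the two percentages would nearly coincide.

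**What to change.** In 7.11.2, keep the planned count as the row for the stated endpoint and add:

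1. One row for treatment-emergent hematology MAV: a post-dose value, scheduled or unscheduled, that meets an Appendix A limit which the same parameter's baseline value did not meet in the same direction. Use the same denominator as for the planned count.
2. A footnote with the number of subjects whose baseline is missing, and a statement of how they are counted. Counting their post-dose MAVs in the new row is workable if the footnote lets a reader take them out. This is a counting rule that imputes no value, so it is compatible with 7.1.6.
3. A baseline-MAV flag in the planned subject mapping. For flagged subjects, show the baseline and the most extreme post-dose value, so that worsening from an abnormal baseline stays visible.

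A separate 11-line cross-table is not needed at this sample size. The cost is a short SAP paragraph, one row, one footnote and one flag from data already collected, plus a second percentage to explain. The stated endpoint, its count and its denominator do not change.
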